**Notes:**

- Patients who discontinue study drug for reasons other than PD (e.g., AE, noncompliance, etc.) may (but, for practical reasons and to minimize patient inconvenience, are not required to) have scans performed and collected as defined above.

- Post-baseline imaging of the brain using the same modality as at baseline should be performed for patients with evidence of CNS disease at baseline and if clinically indicated.
- If consistent with local regulatory guidelines, an initial post-baseline assessment after 4 weeks of treatment ( $\pm 7$  days) is encouraged. If this scan is performed, the next scan should continue according to the schedule above (beginning at C3D1).
- If consistent with local regulatory guidelines, confirmatory imaging a minimum of 4 weeks (e.g., 28 days) after the first imaging studies that demonstrate a tumor CR or PR by RECIST 1.1 or RANO is encouraged. If this scan is performed, the next scan should continue according to the schedule above.
- Outpatient diaries for recording daily selpercatinib dosing, PPIs, H2 blockers, and antacids (refer also to Restricted Concomitant Medications, Section 6.3.3).
- AEs.
- Concomitant medications.
- Patient-reported outcomes:
  - For MTC patients with diarrhea present at baseline: bowel diary, Day 1 of each cycle starting with C2.
  - For patients 18 years or older: EORTC QLQ-C30 completed at the same cycle visits as disease assessments until EOT.
  - For patients age 13 to 17 years: PedsQL for teens completed at the same cycle visits as disease assessments until EOT.
  - For patients age 12 years: PedsQL for children completed at the same cycle visits as disease assessments until EOT.

#### 7.4 Intra-Patient Dose Escalation

As discussed in Section 3.4, intra-patient dose escalation may be permitted by the Sponsor following completion of the 28-day DLT period in Cycle 1. Please note that this guidance applies to Phase 1 intra-patient dose escalation, and does not apply to patients who dose reduce and are re-escalated to the starting dose.

The following procedures will be performed (refer to Table 7-1):

- Day 1 of new dose ( $\pm 3$  days):
  - Symptom-directed physical examination, weight, and ECOG or Lansky score.
  - Vital signs.
  - Resting 12-lead ECGs: pre-dose, up to 4 hours pre-dose, 2 hours postdose- ( $\pm 10$  minutes). Further ECGs may be required based upon results of the 2 hours post-dose ECG (refer to Table 7-1, footnote “j” for specific instruction based upon QTcF value observed).
  - Hematology (as described in Section 7.1).
  - Serum chemistries (as described in Section 7.1).
- Day 8 of new dose ( $\pm 3$  days):
  - Symptom-directed physical examination, weight, and ECOG or Lansky score.

- Vital signs.
- Resting 12-lead ECG: 2 hours post-dose ( $\pm 10$  minutes) prior to blood draw for PK sample if performed at this time point. Further ECGs may be required based upon results of the 2 hours post-dose ECG (refer to [Table 7-1](#), footnote “j” for specific instruction based upon QTcF value observed).
- LFTs (as described in Section [7.1](#)).
- Blood sample for PK (2 mL whole blood): pre-dose (within 1 hour prior to dosing) and post-dose at 1, 2 and 4 hours ( $\pm 15$  minutes) and 8 hours ( $\pm 30$  minutes).

If Day 1 of the new dose falls on the same day ( $\pm 3$  days) of a previous hematology and serum chemistry assessment, and LFTs, it is not necessary to perform a repeat assessment (exam, vital signs, and ECGs must still be performed as indicated). Patients found to have treatment-emergent laboratory toxicity of Grades 3 or 4 will be monitored at least weekly until resolution.

Requests for intra-patient dose escalation must be made to the Sponsor prior to treating a patient with a new dose. Treatment with a new dose should start on Day 1 ( $\pm 3$  days) of a cycle unless discussed with the Sponsor.

Exceptions to these assessments will not be considered protocol violations if approved by the Sponsor.

## **7.5 End of Treatment Visit (All Patients)**

Within 7 days of last dose of study drug or at the time of premature discontinuation of treatment, the following procedures will be performed:

- Scheduling of tumor tissue biopsy from patients who experience PD (optional and if it can be safely performed in the judgement of the Investigator).
- Symptom-directed physical examination, weight, and ECOG or Lansky score.
- Vital signs.
- Resting 12-lead ECG: only if prior ECG reading showed treatment-emergent abnormalities.
- Hematology (as described in Section [7.1](#)).
- Serum chemistries (as described in Section [7.1](#)).
- Pregnancy test for women of childbearing potential (surgically sterilized females or those who have not experienced menses for at least 2 years are not required to be tested).
- LFTs (as described in Section [7.1](#)).
- Urinalysis.
- Calcitonin, CEA: for patients with MTC only. For each patient, these should be performed in the same laboratory as prior testing to minimize intra-patient variability in measurement.
- Thyroglobulin: for patients with non-MTC thyroid cancer only (unless not measurable due to presence of anti-thyroglobulin antibodies). For each patient, all tests for

thyroglobulin should be performed in the same laboratory to minimize intra-patient, lab-to-lab variability in their measurement.

- Serum cortisol, serum ACTH, 24-hour urine for free cortisol: optional for patients with Cushing's disease related to their cancer.
- Whole blood for cfDNA analysis: obtained at the EOT visit even if radiologic disease assessment is not performed.
- Radiographic disease assessment (if not performed within the last 2 cycles). Patients who have an ongoing CR or PR and discontinue study drug for reasons other than PD (e.g., AE, noncompliance, etc.), may (but, for practical reasons and to minimize patient inconvenience, are not required to) have scans collected ~ every 8–12 weeks as outlined above until documented PD.
- Return unused selpercatinib.
- Outpatient diaries for recording daily selpercatinib dosing, H2 blockers, and antacids.
- AEs.
- Concomitant medication(s).
- Patient-reported outcomes:
  - For MTC patients with diarrhea present at baseline: Bowel diary.
  - For patients 18 years or older: EORTC QLQ-C30.
  - For patients age 13 to 17 years: PedsQL for teens.
  - For patients age 12 years: PedsQL for children.

## 7.6 Safety Follow-Up Visit

Twenty-eight (28) days (+7 days) after the final dose of study drug (may be performed as part of the EOT visit if the latter was performed at least 28 days after final dose of the last cycle), the following will be performed:

- Symptom-directed physical examination, weight, and ECOG or Lansky score.
- Vital signs.
- Resting 12-lead ECG.
- Hematology (as described in Section 7.1).
- Serum chemistries (as described in Section 7.1).
- Pregnancy test for women of childbearing potential (surgically sterilized females or those who have not experienced menses for at least 2 years are not required to be tested).
- LFTs (as described in Section 7.1).
- Urinalysis.
- AEs.
- Status of unresolved SAEs (if unresolved SAEs exist at the time of this visit, subsequent assessment for resolution may be conducted by phone if the patient is not able to return to the clinic).

- Concomitant medication(s).

## **7.7 Long-Term Follow-Up**

After treatment discontinuation, LTFU will occur approximately every 3 months ( $\pm 1$  month) until the patient has withdrawn consent for further participation, is lost to follow-up, has died, or the Sponsor makes a decision to close the study. Assessments may include: subsequent anticancer therapy(ies) and survival status. LTFU may be conducted by phone. For any patient who is lost to follow-up, the study site will attempt to ascertain survival information via public database search. If survival status still cannot be ascertained, patients will be considered lost to follow-up and will be censored appropriately.

## **7.8 Procedures for Special Tests**

### **7.8.1 Tumor Measurements**

Tumors will be assessed by the Investigator according to the guidelines provided in Section 7 and the Imaging Manual. Investigators should use the same method consistently for an individual patient throughout the study. Assessments of both measurable and non-measurable disease will be made by the Investigator using RECIST 1.1 (refer to [Appendix G](#)) or RANO criteria ([Appendix H](#)) as appropriate to tumor type; or a comparable assessment method depending on location of tumor.

### **7.8.2 Central Collection of Radiographic Studies**

Baseline screening radiographic studies and all subsequent radiographic studies and their associated reports will be collected and stored for future independent radiological review.

### **7.8.3 Pharmacokinetics**

Plasma samples will be obtained for patients as outlined in Section 7. Additional PK assessments may be conducted in patients when considered necessary by the Investigator to understand exposure in relationship to possible safety or efficacy findings or if there is a change to the formulation of selpercatinib administered. Samples will be collected and handled as outlined in the Laboratory Manual, and concentrations of selpercatinib will be determined with a validated bioanalytical method. These data will be used to determine parameters such as  $AUC_{0-t}$  and plasma terminal elimination half-life ( $t_{1/2}$ ). The 0-8-hour duration of sample collection will be sufficient to cover a significant fraction of the area under the plasma concentration versus time curve.

Plasma samples will be obtained on C1D8 and D8 of a patient's new dose (if the patient is intra-patient dose escalated). PK parameters calculated from the drug concentrations in these samples will be used to compare the area under the concentration versus time curve from time 0 to infinity ( $AUC_{0-\infty}$ ) on D1 with the area under the concentration versus time curve calculated during the dosing interval at steady state ( $AUC_{\tau}$ ) and detect any auto-inhibition or auto-

induction of the PKs of selpercatinib (none is expected). Exploratory analyses to determine the presence and structures of metabolites of selpercatinib may also be conducted and the results of these analyses, if conducted, will be reported separately by the Sponsor.

#### **7.8.4            *Collection of EORTC QLQ-C30, PedsQL for Teens, PedsQL for Children, and Bowel Diary***

Paper HRQoL instruments will be administered pre-dose on C1D1.

The EORTC QLQ-C30, PedsQL for teens, or PedsQL for children questionnaires and a bowel diary (for MTC patients only) will be used as appropriate for the patient (refer to [Appendix I](#)) and should be implemented for newly enrolled patients. Only patients who have completed questionnaires at baseline should complete subsequent questionnaires at the specified follow-up periods.

For EORTC QLQ-C30, PedsQL for teens, or PedsQL for children, subsequent assessments will occur at the same cycle visits as disease assessments until EOT. Each assessment should be performed before the subject learns the results of his or her restaging.

For MTC patients, the bowel diary assessments will be collected weekly on Cycle 1, and on Day 1 of every cycle thereafter through EOT. Inaccurate recording will not be considered a protocol violation.

#### **7.8.5            *Correlative Studies***

##### **7.8.5.1            Archived Tumor Samples**

Archived tumor samples prior to treatment with selpercatinib are required if available for participation in the trial. Tissue blocks are preferred, otherwise ~25 × 5 um unstained slides, with verification of at least 20% tumor content, should be provided. If sufficient quantity or quality of tissue cannot be provided, patients should undergo a fresh tumor biopsy, if it is considered safe to perform, prior to treatment (refer to Section 7.8.5.2). The samples will be used for identification or confirmation of molecular abnormalities in *RET* and other genes.

The sample collection must be captured on the appropriate eCRF and requisition page(s). Refer to the Laboratory Manual for detailed sample collection, storage, and shipment information.

##### **7.8.5.2            Fresh Tumor Biopsies**

Fresh tumor samples will be used to identify putative mutations arising in the *RET* gene (or other genes) that may confer acquired resistance to selpercatinib (or prior MKIs with anti-RET activity) and for other investigations into potential causes of acquired resistance. Fresh tumor biopsies are strongly encouraged when the Investigator feels it is appropriate and safe to do so.

***Prior to selpercatinib treatment***

Required: A fresh tumor biopsy be obtained prior to selpercatinib for all patients who do not have archival tumor tissue available (or who have insufficient tissue quantity or quality—refer to Section 7.8.5.1) and for whom, in the opinion of the Investigator, a fresh tumor biopsy can be safely performed. If archived tumor tissue is not available and a fresh biopsy cannot be safely performed, the patient may still be eligible with prior Sponsor approval.

Optional: If archived tumor tissue was obtained prior to progression on the last MKI with anti-RET activity, a fresh biopsy of a lesion may be obtained if the patient provides informed consent and it can be safely performed. The purpose of the fresh tumor biopsy is to identify genetic alterations related to progression after the previous MKI(s).

***At progression after treatment with selpercatinib***

Optional: A fresh biopsy of a lesion should be obtained if oligometastatic disease constituting progression on selpercatinib is identified, the patient provides informed consent, and it can be safely performed. The purpose of the fresh tumor biopsy is to evaluate tumor changes that may have resulted from treatment.

Optional: A fresh biopsy of a lesion should be obtained if overt progression on selpercatinib is reported, the patient provides informed consent, and it can be safely performed. The purpose of the fresh tumor biopsy is to evaluate tumor changes that may have resulted from treatment.

The biopsy (Table 7-3 ) must be captured on the appropriate eCRF and requisition page(s). Refer to the Laboratory Manual for detailed sample collection, storage, and shipment information.

**Table 7-3 Tissue/Whole Blood Sampling upon Progression**

For patients who progress during therapy, biopsy upon progression should be done if clinically safe to perform and if the patient consents. The clinician should consider if study therapy will continue beyond progression or be discontinued due to progression.	
Scenario	Sampling
At time of progression where study therapy will be discontinued	Tumor tissue sample from patients who experienced PD and consent to biopsy, if it does not jeopardize the patient's health Whole blood for cfDNA analysis
At any progression, including if the patient will continue study therapy as treatment beyond progression	Whole blood for cfDNA analysis Optional tumor biopsy

Abbreviations: cfDNA = circulating free tumor DNA; PD = progressive disease.

**7.8.5.3      Blood Biomarkers**

Whole blood will be collected for evaluating cfDNA pre-dose C1D1, C1D15 and C2D1; and at the time of progression and/or EOT. If oligometastatic disease constituting progression is

identified but the patient is otherwise stable and will continue selpercatinib beyond progression, patients should continue to have blood collected for cfDNA analysis (refer to Laboratory Manual) at the time of each progression, to evaluate tumor changes that may have resulted from treatment.

If overt progression is reported and study drug therapy will be discontinued (i.e., EOT), patients should have blood collected for cfDNA analysis (refer to [Table 7-3](#) to evaluate tumor changes that may have resulted from treatment.

The primary purposes of collection of blood for cfDNA analysis are to identify early indicators of selpercatinib treatment efficacy (e.g., by measuring a decrease in cfDNA) and to identify potential mechanisms of resistance through the identification of new genetic alterations that arise in the *RET* or other genes at progression after treatment with selpercatinib.

In addition, a whole blood sample collected at Screening may be used for DNA sequencing to determine the somatic or germline origin of mutations identified from analysis of archival or fresh tumor samples. Biomarker analyses will not produce interpretable results on germline DNA and therefore no incidental findings will be reported.

The sample collection must be captured on the appropriate eCRF and requisition page(s). Refer to the Laboratory Manual for detailed sample collection, storage, and shipment information.

#### 7.8.5.4 ***Biomarker Samples***

Archived tumor, fresh biopsy, and blood samples may be assessed by various methods including gene panel sequencing and DNA candidate gene studies. Regardless of the technology utilized, data generated will be used only for the specific genomic research scope described in the study objectives or to develop research methods and validate new diagnostic tools or assays.

#### 7.8.6 ***Growth Plate Monitoring***

Participants who have not yet obtained full adult height will undergo radiograph of one knee at baseline and every 6 months while the growth plate remains patent. Whichever knee is imaged at baseline should be imaged at all time points.

Adolescents who have had a documented growth rate of <1 cm/year over the prior 2 years and/or have reached a midparental height of over 152 cm in girls and 167 cm in boys are likely to have obtained full adult height. If it is unclear that a patient has obtained full adult height, pretreatment tibial radiographs (AP and lateral views) of the right knee should be obtained to determine if the growth plate remains patent. If the growth plate remains patent, the patient will have radiographs performed every 6 months until the growth plate is no longer patent. Follow-up MRI is recommended for any unexpected abnormalities identified on radiographs.

### **7.8.7      *Thyroid Function***

Hypothyroidism was reported in patients receiving selpercatinib in clinical trials. Monitor patients for hypothyroidism and treat as medically appropriate. Baseline laboratory measurement of thyroid function is recommended in all patients. Patients with pre-existing hypothyroidism should be treated as per standard medical practice prior to the start of selpercatinib treatment. All patients should be observed closely for signs and symptoms of thyroid dysfunction during selpercatinib treatment. Thyroid function should be monitored periodically throughout treatment with selpercatinib. Patients who develop thyroid dysfunction should be treated as per standard medical practice, however patients could have an insufficient response to substitution with levothyroxine (T4) as selpercatinib may inhibit the conversion of levothyroxine to liothyronine (T3) and supplementation with liothyronine may be needed.

### **7.9              Continued Access**

Participants who are still on study intervention at the time of study completion may continue to receive study intervention in the continued access period if they are experiencing clinical benefit and no undue risks. The continued access period will apply to this study only if at least 1 participant is still on study treatment when study completion occurs. The Sponsor will notify investigators when the continued access period for each participant begins based on cohort assignment or other relevant parameters.

Participants are not required to sign a new ICF before treatment is provided during the continued access period; as of Protocol Amendment 11, the ICF includes information on continued access.

The participant's continued access to study treatment will end when a criterion for discontinuation is met (Section 6.4). Continued access follow-up will begin when the participant and the investigator agree to discontinue study treatment and lasts approximately 30 days ( $\pm 7$ ).

Follow-up procedures will be performed as shown in the Continued Access SoA (see [Table 7-2](#)).

Participants who are in short-term follow-up when the continued access period begins will continue in short-term follow-up until the 30-day short-term follow-up visit is completed. Participants who are in long-term follow-up when the continued access period begins will be discontinued from study.

During Continued Access, long-term follow-up does not apply. Survival and progression information will be collected only for MTC patients (see [Table 7-2](#)).

In all cases, no follow-up procedures will be performed for a participant who withdraws informed consent unless he or she has explicitly provided permission and consent.

## 8. PLANNED ANALYSES

A full Statistical Analysis Plan (SAP) will provide specific details on the analytical methods and data displays.

### 8.1 Study Endpoints

#### *Primary Endpoint (Phase 1)*

- MTD/RP2D

#### *Secondary Endpoints (Phase 1)*

- Frequency, severity, and relatedness of TEAEs and SAEs, changes in hematology and blood chemistry values, assessments of physical examinations, vital signs, and ECGs
- Plasma concentrations of selpercatinib and PK parameters, including but not limited to area under the concentration versus time curve from time 0 to 24 hours ( $AUC_{0-24}$ ),  $C_{max}$ , time to maximum plasma concentration ( $T_{max}$ ), and degree of accumulation
- ORR based on RECIST 1.1 or RANO, as appropriate to tumor type

#### *Primary Endpoint (Phase 2)*

- ORR based on RECIST 1.1 or RANO, as appropriate to tumor type, assessed by IRC

#### *Secondary Endpoints (Phase 2)*

- Parameters of anti-tumor activity/clinical benefit, including: ORR (by Investigator), best change in tumor size from baseline (by IRC and Investigator), DOR (by IRC and Investigator), CNS ORR (by IRC), CNS DOR (by IRC), time to any and best response (by IRC and Investigator), CBR (by IRC and Investigator), PFS (by IRC and Investigator), and OS
- Frequency, severity, and relatedness of TEAEs and SAEs, changes in hematology and blood chemistry values, and assessments of physical examinations, vital signs, and ECGs
- Plasma concentrations of selpercatinib and PK parameters, including but not limited to  $AUC_{0-24}$ ,  $C_{max}$ , and  $T_{max}$

#### *Exploratory Endpoints*

- Differences in efficacy and safety based on selpercatinib PK parameters
- Changes in CEA and calcitonin (patients with MTC), thyroglobulin (non-MTC thyroid cancer patients), and ACTH and cortisol (patients with Cushing's disease related to their cancer) with selpercatinib treatment
- Identity of *RET* gene fusions, mutations, and concurrently activated oncogenic pathways in tumor biopsies and cfDNA
- Changes from baseline in disease-related symptoms and HRQoL, as measured by EORTC QLQ-C30 (adults), PedsQL for teens (ages 13-17 years), PedsQL for children (age 12 years), and patient bowel diaries (MTC patients only)

## **8.2 Analysis Populations**

Handling of missing, unused, and spurious data is addressed prospectively in the overall statistical methods described in the protocol and in the SAP, where appropriate. Adjustments to the planned analyses are described in the final CSR.

### **8.2.1 Safety Analysis Set**

The Safety Analysis Set will be used for the analysis of safety data and will consist of all enrolled patients who receive at least one dose of selpercatinib. A baseline measurement of at least one laboratory or other safety-related measurement obtained after treatment of study drug may be required for inclusion in the analysis of a specific safety parameter.

The analysis populations for other trial objectives (e.g., PK, tumor markers) will be defined in the Statistical Analysis Plan.

## **8.3 Determination of Sample Size**

### *Phase 1*

Three to 6 patients will be enrolled in each dose cohort based on a 3+3 design. Each patient will participate in only a single dose cohort for the purpose of DLT evaluation (though, as discussed in Section 3.4, after completion of the DLT evaluation period, intra-patient dose escalation may be permitted, provided that the patient is tolerating their current dose, and the dose level to which the patient will be escalated has already been evaluated, has a DLT rate of < 33%, and has been declared safe by the SRC).

A starting sample size of at least 3 patients per dose cohort, expanding to 6 patients in the event of a marginal DLT rate (30%) was deemed to be a safe and conventional approach in the dose escalation of a novel oncologic agent. Assuming a true DLT rate of 5% or less, there would be a 3% chance that dose escalation would be halted in a given cohort (i.e., observing 2 or more patients with DLT). If a true DLT rate of 50% is assumed, then there would be an 89% chance that dose escalation would be halted in a given cohort.

During Phase 1, selected dose cohorts previously declared safe by the SRC may be expanded to a total of approximately 15 patients to further investigate the tolerability, PK, and biological activity of selpercatinib.

The total number of patients to be enrolled in Phase 1 is dependent upon the observed safety profile, which will determine the number of patients per dose cohort, as well as the number of dose escalations required to achieve the MTD/RP2D for further study. If approximately 15 patients are enrolled in each planned dose cohort (Cohorts 1–8), a total of approximately 120 patients will be enrolled in Phase 1.

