**Table 3-1 Actual Dose Escalations for Selpercatinib**

Level	Dose	Frequency	Total Daily Dose
1	20 mg	QD	20 mg
2	20 mg	BID	40 mg
3	40 mg		80 mg
4	60 mg		120 mg
5	80 mg		160 mg
6	120 mg		240 mg
7	160 mg		320 mg
8	240 mg		480 mg
9	200 mg		400 mg
Additional potential doses			
10 and higher	Per SRC	TBD	TBD

Abbreviations: BID-twice daily; mg-milligram; QD-once daily; SRC-Safety Review committee; TBD-to be determined.

A meeting of the SRC will be convened for each cohort dose escalation decision (see Section 9.1). For each cohort dose escalation decision, the SRC will recommend the dose for escalation, determination of DLT(s) recommended dose for further study. Smaller dose escalation increments will be considered in the event of frequent, unexpected AEs or DLTs as noted below.

A minimum of 3 patients in a given cohort must have completed 28 days of safety assessment in C1 without DLT, and a maximum of one DLT may be seen in 6 patients who have completed the DLT window before the next cohort initiates accrual.

Dose escalation will follow the 3+3 design. A minimum of 3 and a maximum of 6 persons will be concurrently enrolled into a single dosing cohort, depending on the occurrence of DLTs.

Each patient in a given cohort must have completed safety assessments through the first 28 days of treatment in C1, and received a minimum of 75% (e.g., 42/56 doses with BID dosing) of the planned total dose during that time (unless due to toxicity) to be eligible for the assessment of a DLT. Patients who receive less than 75% of planned doses due to reasons other than a DLT will be replaced for the determination of the MTD but will remain part of the safety population if they received at least one dose of study drug.

If 3 patients in a dosing cohort are evaluable for toxicity (i.e., have completed 28 days of safety assessment in C1 and have received at least 75% of planned doses) and no DLT has been observed, the next three patients may be enrolled to the next higher dose level with approval of the SRC.

If one patient within a three-person dosing cohort experiences a DLT, then a total of 6 patients will be enrolled to that cohort for the purposes of DLT evaluation. If none of the additional patients have a DLT (i.e., 1 of 6 patients), then enrollment to the next higher dose level may

begin with approval of the SRC. If  $\geq 2$  patients within a dose escalation cohort experience a DLT, then the DLT Dose Level has been reached, and dose escalation will be stopped.

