**Table 3-2 Selpercatinib Participant Enrollment Schema for Dose-Limiting Toxicity (DLT) Evaluation**

Criteria	3+3
Minimum number of patients per cohort	3
Maximum number patients per cohort	6*
Criteria to increase from 3 to 6 patients	1/3 DLTs
Criteria to escalate dose	0/3 DLTs OR 1/6 DLTs
Criteria to stop dose escalation	≥ 2 DLTs
Criteria to de-escalate dose cohort	≥ 2 DLTs at current dose level and < 33% DLT rate in previous dose level
Maximum tolerated dose	≤ 1/6 DLTs

\*See above for situations warranting accrual of additional patients.

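### The 89% chance of halting escalation at a 50% DLT rate assumes six patients in every cohort; the protocol's own 3+3 rule gives 83%

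*Protocol*

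**What the plan says.** The Phase 1 part of Protocol Section 8.3 sets out the design: "Three to 6 patients will be enrolled in each dose cohort based on a 3+3 design". The starting size is at least three, rising to six when the DLT rate is marginal. Halting is defined there as "i.e., observing 2 or more patients with DLT". Two probabilities follow, each for a single cohort:

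- Low rate: "Assuming a true DLT rate of 5% or less, there would be a 3% chance that dose escalation would be halted in a given cohort".
- High rate: "If a true DLT rate of 50% is assumed, then there would be an 89% chance that dose escalation would be halted".

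The decision rule is in Section 3.4. With three evaluable patients, if "no DLT has been observed, the next three patients may be enrolled to the next higher dose level with approval of the SRC". One DLT among three leads to a total of six patients. Two or more DLTs stop escalation. Table 3-2 agrees: its row "Criteria to escalate dose" lists 0/3 or 1/6, and its row for going from three to six patients lists 1/3.

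The SAP does not discuss Phase 1 escalation, so it neither repeats nor corrects the 89%.

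**The concern.** The two probabilities are the only operating characteristics the protocol gives for the escalation rule, and the 89% is the one that speaks to protection at a toxic dose. It matches a calculation in which every cohort has six patients. Under the 3+3 rule, a cohort whose first three patients have no DLT moves on, and three further patients who might have shown toxicity are not required. Leaving out that branch makes the rule look more protective than it is. A reader judging the design from Section 8.3 would take the chance of passing a level toxic in half of patients to be about 11%.

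**Working it through.** **Inputs.** True DLT rate p = 0.50 or 0.05, and halting means two or more DLTs (Section 8.3). Escalate after 0/3, expand to six after 1/3, escalate after 1/6, stop at two or more (Section 3.4 and Table 3-2). Patients are taken as independent with a common DLT rate, all evaluable, and the rule is applied as written.

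**Step 1: reproduce the stated figures.** With a fixed six patients,

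P(halt) = 1 − (1−p)^6 − 6p(1−p)^5.

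- p = 0.50: 1 − 1/64 − 6/64 = 57/64 = 0.8906, the stated 89%.
- p = 0.05: 1 − 0.7351 − 0.2321 = 0.0328, the stated 3%.

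**Step 2: rule out other sources of the 89%.** At p = 0.50, two or more DLTs in a fixed three, four or five patients gives 50.0%, 68.8% and 81.3%. Halting on one or more DLTs in three gives 87.5%, but 14.3% at p = 0.05, and it contradicts the stated criterion of two or more. Of the variants tried, only two or more in a fixed six reproduces both stated figures.

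**Step 3: apply the 3+3 rule.** A cohort escalates if the first three patients have no DLT, or if they have exactly one and the next three have none:

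P(escalate) = (1−p)^3 + 3p(1−p)^2 × (1−p)^3, and P(halt) = 1 − P(escalate).

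- p = 0.50: 0.125 + 0.375 × 0.125 = 0.1719, so P(halt) = 0.8281.
- p = 0.05: 0.8574 + 0.1354 × 0.8574 = 0.9734, so P(halt) = 0.0266.

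Simulation of 400,000 cohorts at each rate gave 0.828 and 0.027.

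**Step 4: account for the gap.** The two calculations differ only when the first three patients have no DLT and three more would have had two or more. At p = 0.50 that is 0.125 × 0.5 = 0.0625, which is exactly 0.8906 − 0.8281. The difference is structural, not rounding.

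| True DLT rate | Stated P(halt) | Fixed six patients | 3+3 rule | P(escalate), fixed six | P(escalate), 3+3 |
|---|---|---|---|---|---|
| 50% | 89% | 89.1% | 82.8% | 10.9% | 17.2% |
| 5% | 3% | 3.3% | 2.7% | 96.7% | 97.3% |

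At the 50% rate the ratio of escalation probabilities is 0.1719 / 0.1094 = 1.57.

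**The case against.** **Six as the cohort size.** Section 3.4 lets up to six people be enrolled concurrently in a cohort, so one might read the 89% as describing a six-patient cohort. That reading fails. The same sentence makes the number depend on whether DLTs occur, 0/3 is sufficient to escalate, and Section 8.3 itself starts from three.

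**Other safeguards.** The rule does not act alone. Escalation after 0/3 or 1/6 needs approval by the Safety Review Committee, which also watches cumulative data from cohorts already declared safe, can use smaller increments, and considers toxicity after the DLT window. This stands as a reason to give the figure limited weight. It does not rescue the 89%, because none of these elements enters that calculation either.

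**Little depends on it.** No sample size or stopping boundary is derived from the 89%; it is illustrative. This stands, and it keeps the severity low.

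**A stronger reading to avoid.** A reader might infer that the recommended Phase 2 dose rests on an overstated safety property. Section 3.6.1 does not support that. It bases 160 mg BID on cumulative PK, safety and efficacy data from 89 patients, 24 of them at that dose. The 0/3 branch was used: 240 mg BID opened after three DLT-evaluable patients at 160 mg BID. However, 20 more patients were enrolled at 160 mg BID as backfill before the selection. At 240 mg BID, 2 of 6 patients had DLTs, which counts as a halt under either calculation. The 200 mg BID level was explored as part of the same decision that selected 160 mg BID, so that selection did not depend on its three patients.

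**The 30% rate.** Section 8.3 mentions 30% only as the marginal rate that prompts expansion to six. It gives no halting probability for it, so there is no figure at that rate to correct.

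**Conclusion.** Wrong as written, low severity. The 89% describes a fixed six-patient cohort, which is not the design in Section 3.4 and Table 3-2. The 3+3 rule gives 82.8% at a 50% DLT rate, about 6 percentage points lower, and the error flatters the design. The 3% figure is unaffected at its stated rounding. The result assumes independent patients with a common DLT rate, no replacement of non-evaluable patients, and the rule followed without committee discretion. The point corrects one stated operating characteristic. It does not change the escalation rule, the observed DLT data or the basis for the selected dose.

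**What to change.** In Protocol Section 8.3, either restate the halting probability at a 50% DLT rate as 83%, or keep 89% and say explicitly that it applies only to a cohort of six evaluable patients. The first option is better because it describes the rule actually specified. The 3% figure can stay. The cost is one sentence and a slightly less favourable number. Escalation is complete, so no procedure, analysis or dose is affected.
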